Title: Modulation of Sensory Acuity With Transcranial Magnetic Stimulation (TMS) (Exp 7)

NCT number: NCT05723575

Document date: 7/18/2024

Study Protocol

This study consists of three related behavioral paradigms aiming to test sensorimotor adaptation, a correlative analysis investigating the relationship between the outcome measurements from these three experiments, and several experiments seeking to modulate these outcome measures. Here we describe Experiment 7, which used transcranial magnetic stimulation (TMS) to modulate somatosensory acuity of the tongue.

Experiment 7 specific Methods: Participants will complete three TMS sessions (iTBS, cTBS, sham) and a fourth behavioral-only control session. Each session will be separated by at least one week with the order counterbalanced across participants. The target of the stimulation is left primary somatosensory cortex (S1). The duration of tbTMS stimulation is short (40-190s), with effects that begin ~5 minutes following stimulation and persist for up to 30 minutes. In each TMS session, sensory acuity will be tested in two tasks (spatial and temporal) before and after application of theta-burst TMS (tbTMS):

- *Task practice:* Participants first complete a brief training to familiarize them with each acuity task and to ensure they met performance criteria (five consecutive correct responses).
- *Baseline tests:* Participants complete 3 blocks of each task, with the tasks alternating.
- *TMS localization and thresholding:* Single-pulse TMS is used to localize the target stimulation site (S1) and determine the active motor threshold. S1 is localized on each participant's brain surface with Brainsight neural navigation by moving the stimulator 2 cm posterior to a motor hotspot that elicits tongue motor-evoked potentials (MEPs).
- *Rest:* 20-minute break to allow the somatosensory cortex to recover from any potential disruption related to single-pulse TMS.
- *TBS:* Delivery of TBS to S1. Stimulation intensity will be set to 80% of the active motor threshold. Sham stimulation will be applied with the coil rotated away from the head (coil facing downward). This emits the same sound as active stimulation without stimulating the brain.
- *Post tests:* Performed every 5 minutes for 45 minutes following stimulation: participants complete 10 blocks of each task (SDT and TDT), alternating between the tasks with a 1-minute break in between each task.

In the 4th behavioral-only session ("control"), participants' acuity is tested without TMS localization.

- *Somatosensory acuity metrics:* The acuity tasks measure tactile acuity (spatial amplitude and temporal order judgment) with a custom corticalmetrics Brain Gauge vibrotactile stimulator. These measures reliably track the recovery of somatosensory function after neurological damage and can be modified with tbTMS. We use tactile acuity as a proxy for full somatosensation, given the difficulty in measuring proprioception in the oral system. Tactile acuity has been suggested to be important for speech production, as tactile contact is maintained parasagittally during vowel production and tactile deprivation leads to imprecise speech movements.
- *Data analysis and outcome measurements:* Each acuity task (spatial amplitude and temporal order judgment) yields a threshold (spatial amplitude discrimination threshold in μ m; temporal discrimination threshold in ms) representing the smallest difference detectable by the participant at a given time point. For each acuity task, we will compare the change in threshold from pre- to post-TMS. Post-TMS values will be normalized by subtracting baseline thresholds for each task on a session-specific basis, then compared across time windows.

- *Sample size with power analysis:* Given previous results in the hand ($d = 1.8-3.1$), we conservatively anticipate an effect size of Cohen's $d = 1$. Testing 17 participants gives a power of .82 with $\alpha = 0.05$.

Statistical Analysis Plan

Experiment 7: We will compare the change in sensory acuity from pre- to post-TMS between sessions using a repeated measures ANOVA. Post-TMS values will be normalized by subtracting baseline thresholds for each task on a session-specific basis, then compared across time windows. To compare changes in thresholds across sessions, a single repeated-measures ANOVA will be conducted for each task with sessions (cTBS, iTBS, control, sham) and time windows as independent variables.

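### Visit position is counterbalanced by design but absent from the planned ANOVA; if all four sessions rotate this can cost power, not validity, so first settle whether control rotates

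*Combined protocol and SAP*

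**What the plan says.** The Experiment 7 methods have every participant attend "three TMS sessions (iTBS, cTBS, sham) and a fourth behavioral-only control session". On order they say: "Each session will be separated by at least one week with the order counterbalanced across participants". The counterbalancing scheme (Latin square, Williams square, or a selection of the 24 possible orders) is not given. The paragraph on the control session opens "In the 4th behavioral-only session", which leaves some doubt about whether control is one of the rotated sessions.

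The outcome is a change score: "Post-TMS values will be normalized by subtracting baseline thresholds for each task on a session-specific basis, then compared across time windows". The Statistical Analysis Plan then fits one repeated-measures ANOVA per task "with sessions (cTBS, iTBS, control, sham) and time windows as independent variables". Visit position (1 to 4) appears nowhere in the model. The documents give no SD, no size for a visit effect and no definition of the time windows.

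**The concern.** Counterbalancing keeps visit effects approximately out of the session means. It does not remove them from the data. In a model without visit they go into the error term.

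Baseline subtraction deals with one kind of visit effect. If a participant simply has a lower threshold at the second visit than at the first, both the baseline and the post-test values move and the change score does not. It does not deal with a change that itself depends on visit. Learning or fatigue over the 45-minute post-test, with its ten blocks of each task, could be larger at the first visit. The documents do not say that this happens.

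What is at stake depends on a point the documents leave open. If all four sessions rotate, a visit-dependent change lowers power in a 17-person study. If control is always the last visit, the same effect separates control from the other three sessions and can look like a session effect.

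**Working it through.** **Inputs from the documents.** 17 participants; four sessions; alpha 0.05; Cohen's d = 1; stated power .82. Model factors: session and time window.

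**The plan's own figure.** With n = 17 and d = 1, a two-group normal approximation with 17 per group gives 0.830, and the t-based version gives 0.807. A paired t-test gives 0.972 if d is in SDs of the paired difference. If d is in single-score SDs, it gives 0.781 with uncorrelated sessions and 0.822 with correlation 0.1. So .82 can be approached in more than one way and does not identify the scale of d. Both scales are used below: 1 paired SD, and 1/√2 = 0.71 paired SD.

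**Session error term, all four sessions rotating.** Set the paired-difference SD to 1, so the residual variance per session is 0.5. Assume the change at the first visit differs by δ from the other three. Within a participant this adds δ²(1 − 1/4) = 0.75δ² to the sum of squares, or 17 × 0.75δ² = 12.75δ² in total. With balanced positions nearly all of it falls in the (17 − 1)(4 − 1) = 48 error df:

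error MS = 0.5 + (12.75/48)δ²; SE of a session contrast = √(2 × MS/17).

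| δ (paired SD) | Error MS | SE, formula | SE, simulated | SE with visit |
|---|---|---|---|---|
| 0 | 0.500 | 0.243 | 0.241 | 0.242 |
| 0.25 | 0.517 | 0.246 | 0.245 | 0.242 |
| 0.5 | 0.566 | 0.258 | 0.257 | 0.242 |
| 1 | 0.766 | 0.300 | 0.299 | 0.242 |

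The simulation used a Williams square, four participants per sequence, with the 17th placed in each sequence in turn.

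- *Omnibus session F (the planned test).* Type I error is about 0.03 at δ = 0.5 and 0.01 at δ = 1, against 0.05 with visit. With iTBS alone differing by 0.71 paired SD, power is 0.83 and 0.82 at δ = 0 and 0.25, just under 0.80 at 0.5 and 0.61 at 1. With visit it is about 0.83.
- *iTBS-sham contrast with pooled error (not named in the plan; shown for scale).* At 0.71 paired SD, power is 0.81 / 0.81 / 0.78 / 0.66 across the four values of δ, against 0.81 with visit. At 1 paired SD it is 0.98 / 0.98 / 0.97 / 0.94, against 0.98.

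**A different shape.** Let the change follow a linear trend of range R over the four visits, in residual SD units (residual variance 1). The visit sum of squares per participant is (20/36)R², so the error MS rises by 17 × (20/36)R²/48 = 0.197R²: 5%, 20% and 79% at R = 0.5, 1 and 2. Simulated omnibus type I error is 0.042, 0.029 and 0.005. Power falls from 0.83 to 0.80, 0.71 and 0.40, and returns to about 0.83 with visit.

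**Session-by-window error term.** A visit effect that is constant over windows leaves this test unaffected; only one that varies across windows enters it. Assumptions: 10 windows, an iTBS effect of 0.9 per-window SD in the 5- to 30-minute windows, residual SD 1, and participant-by-session and participant-by-window SD 0.5. For a first-visit drift rising to 0, 1 and 2 per-window SD by the last window, planned power is 0.81 / 0.78 / 0.67, against 0.80 throughout with visit-by-window. Type I error is 0.05 / 0.04 / 0.02, against 0.05. A visit main effect alone changes nothing here.

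**If control is always last.** With the other three sessions rotating over visits 1 to 3, a first-visit effect δ puts δ/3 into each of their means and nothing into control. A linear trend of range R separates control from them by R/2 − (−R/6) = 2R/3. In paired SD, that is 0.17 and 0.33 for δ = 0.5 and 1, and 0.33 and 0.67 for R = 0.5 and 1. Simulated omnibus type I error is 0.07 and 0.10 for the first-visit step, and 0.23 and 0.71 for the trend. A four-level visit factor cannot repair this: visit and control are aliased (rank 22 with 23 columns).

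**The case against.** The strongest reply is that nothing here is an error. Session and window factors on a counterbalanced design give a valid test. The sessions are at least a week apart, TMS sessions begin with practice to a criterion and three baseline blocks per task, and baseline subtraction removes level shifts. What is left is a visit effect on the change itself, for which the documents offer no evidence. The drift needed is also large: 1 paired SD equals the whole anticipated effect if d = 1 is on that scale, and even then the contrast power is 0.94. This stands as to importance, and is why the point is only an optional improvement.

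A second reply also stands. Visit cannot be added as another crossed within-subject factor in a default repeated-measures ANOVA, because each participant fills only 4 of the 16 session-by-visit cells. A careless replacement can do more harm than the drift: omitting participant-by-window variation cut session-by-window power from 0.81 to 0.51 with no drift at all.

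Three stronger readings are tempting, and the documents support none of them:

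- *The planned test is biased.* Not if all four sessions rotate; type I error is then at or below 0.05.
- *The test is conservative whatever was done.* That needs control to rotate and positions to be balanced. With fully random orders type I error stays near 0.05 (0.048 to 0.058) and only power falls.
- *Control was fixed as the last visit.* The numbering may simply count a fourth kind of session. The sentence on order covers each session, so rotation of all four is the more natural reading.

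**Conclusion.** The point holds as a conditional precision refinement. If all four sessions rotate, leaving visit out costs power when the pre-to-post change differs by visit. The loss is small below about 0.5 paired SD, or below about 1 per-window SD of drift for session-by-window, and becomes material near 1 paired SD (omnibus power 0.61 against about 0.83 at a 0.71 paired SD effect). Validity is not in question on that reading. If control was always last, the session test can instead be anti-conservative, and that matters more than the precision loss.

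Every visit-effect size, the number of windows and the variance components are assumptions; only the sample size, number of sessions, alpha, d and model factors come from the documents. The direction of the result does not depend on the assumed values; its size does.

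**What to change.** 1. State the counterbalancing scheme and whether control rotates through all four positions. Session dates settle this.
2. If control rotates, add visit position (1 to 4) as a fixed factor to each task's analysis, and visit-by-window wherever session-by-window is tested. Use a Latin-square-type ANOVA, or a mixed model that keeps both participant-by-session and participant-by-window variation.
3. If control was always last, base conclusions about stimulation on iTBS, cTBS and sham with visit (1 to 3) in the model, and treat comparisons with control as descriptive.
4. If outcomes have already been analysed, report the adjusted model as a labelled sensitivity analysis.

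**Cost.** No new data are needed. Error df fall from 48 to 48 − 3 = 45 for session and, with 10 windows, from 48 × 9 = 432 to 432 − 27 = 405 for session-by-window. With no visit effect the session test loses about 0.2 to 0.4 percentage points of power (0.814 to 0.812 for the contrast, 0.831 to 0.827 for the omnibus test), and session-by-window goes from 0.806 to 0.804. Non-orthogonality at n = 17 raises the variance of the worst-affected session contrast by 0.3% under a four-sequence square. With 17 of the 24 orders the rise has a median of 3.6% and a maximum of 9.8%. The analysis is no longer a default repeated-measures ANOVA and needs its error structure written out.

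### The SAP's session-by-window ANOVA neither targets the 5-to-30-minute period in which an effect is expected nor says which term decides

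*Combined protocol and SAP*

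**What the plan says.** The design is within-participant: "Participants will complete three TMS sessions (iTBS, cTBS, sham) and a fourth behavioral-only control session". Experiment 7 specific Methods describes theta-burst stimulation as brief, "with effects that begin ~5 minutes following stimulation and persist for up to 30 minutes". Before stimulation, "Participants complete 3 blocks of each task, with the tasks alternating". The post-tests are "Performed every 5 minutes for 45 minutes following stimulation: participants complete 10 blocks of each task", the two tasks alternating with a one-minute break.

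The Statistical Analysis Plan states: "Post-TMS values will be normalized by subtracting baseline thresholds for each task on a session-specific basis, then compared across time windows". It then says that "a single repeated-measures ANOVA will be conducted for each task with sessions (cTBS, iTBS, control, sham) and time windows as independent variables". The number and limits of the windows are not given, and nothing links them to the 5-30 minute period. The plan does not say whether the session main effect, the interaction or a specific contrast answers the question.

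Under Sample size with power analysis, the plan cites d = 1.8-3.1 from work in the hand. It continues "we conservatively anticipate an effect size of" d = 1, and "Testing 17 participants gives a power of .82 with" alpha = 0.05. It does not say which comparison or which post-test blocks that d describes.

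**The concern.** By the protocol's own account, blocks outside 5-30 minutes should carry no effect. A session main effect averages over every block, so the empty blocks dilute it. The interaction responds to the shape over time, so it keeps most of the signal. But it answers a different question (do the session profiles differ?) and does not estimate the change in the expected period. It is also sensitive to serial correlation between closely spaced blocks.

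The same data could therefore give different answers depending on the term read, and the plan leaves that choice open. At stake are power if the main effect is used, and false-positive control if the interaction is used uncorrected or if either term may count as success.

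**Working it through.** **The stated power.** With 17 per independent group, d = 1 and two-sided alpha 0.05, the exact t-test gives 0.807 and the normal approximation 0.830, so .82 is matched within two points. A paired t-test with a standardised paired difference (dz) of 1 and n = 17 gives 0.972. The figure does not show which blocks d = 1 refers to.

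**Share of blocks.** Ten blocks every 5 minutes for 45 minutes fit 0, 5, ..., 45. Those at 5, 10, 15, 20, 25 and 30 fall inside the expected period: 6 of 10. The ten-block mean change is then 0.6 of the 5-30 minute change. Pooling blocks into equal-sized windows does not alter this.

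**Standardised effect.** Assumptions, none stated in the documents:
- a constant effect at 5-30 minutes and none outside;
- dz = 1 on the six-block mean;
- the mean of three baseline blocks subtracted.

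With independent block noise of variance s²:
- variance of the six-block change = s²(1/6 + 1/3) = 0.500 s²
- variance of the ten-block change = s²(1/10 + 1/3) = 0.433 s²
- ten-block dz = 0.6 × √(0.500/0.433) = 0.645

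For AR(1) noise at 0.5, 0.7 and 0.9, ten-block dz is 0.643, 0.637 and 0.617 if the baseline is uncorrelated with the post-tests, and 0.657, 0.644 and 0.606 if it directly adjoins them. The overall range is 0.606-0.657.

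**Session test.** F with 3 and 48 degrees of freedom, n = 17, noncentrality 34 × dz² × c. Here c is the sum of squared deviations of the four session effects, in units of the active effect. Example: 34 × 0.645² × 0.75 = 10.6, giving power 0.75.

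| Pattern | c | Ten-block main effect | 5-30 min mean |
|---|---|---|---|
| One active session | 0.75 | 0.69-0.77 | 0.99 |
| Two equal, same direction | 1 | 0.82-0.89 | above 0.99 |
| Two equal, opposite | 2 | 0.99 | 1.00 |
| Second at half strength, same direction | 0.6875 | 0.65-0.73 | 0.98 |
| Second at half strength, opposite | 1.1875 | 0.89-0.94 | 1.00 |

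**Sensitivity, one active session.** Power is 0.53-0.61 with 5 of 10 blocks active, 0.82-0.86 with 7 of 10, and 0.93-0.95 if half the effect is present outside 5-30 minutes. If d = 1 already describes the ten-block mean, main-effect power is 0.99. If d = 1.8 on the 5-30 minute mean, 0.6 × 1.8 = 1.08 and power is above 0.99.

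**Interaction.** Simulated with 17 participants × 4 sessions × 10 blocks; noise independent, or AR(1) at 0.5, 0.7 or 0.9. Power with one active session is 0.90-1.00 with one block per window, 0.77-1.00 with five two-block windows, and 0.94-1.00 with three windows of 3/4/3 blocks. Type I error with ten windows at nominal 5%:

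| Noise | Interaction, uncorrected | Interaction, Huynh-Feldt | Either term, uncorrected | Either term, Huynh-Feldt |
|---|---|---|---|---|
| Independent | 0.052 | 0.049 | 0.099 | 0.096 |
| AR(1) 0.5 | 0.083 | 0.055 | 0.127 | 0.100 |
| AR(1) 0.7 | 0.110 | 0.059 | 0.153 | 0.104 |
| AR(1) 0.9 | 0.148 | 0.059 | 0.189 | 0.105 |

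Under AR(1) 0.5-0.9 the uncorrected interaction rate is 6-10% with five windows and 5-7% with three. The roughly 10% for either term after correction is what two 5% tests give: 1 − 0.95² = 0.0975. A single session test on the 5-30 minute mean held 0.047-0.051 throughout.

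**The case against.** The strongest reply is that the plan is already time-resolved: it compares values across windows and makes window a factor. A collapsed ten-block main effect is only one reading, and the interaction would usually detect the effect. If the undefined windows happen to cover only 5-30 minutes, nothing is diluted. This stands, and it makes the dilution conditional. It does not supply the missing rule.

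Second, the plan's own effect sizes may absorb the loss. Sixty percent of the lowest cited value, 1.8, is 1.08, still above the planning value. With two equally active sessions, main-effect power is at or above the stated .82. These points also stand, though the documents give neither the directions of effect nor the blocks to which d refers, so the favourable cases cannot be relied on.

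Third, exact block times are not given. Two alternating tasks cannot start in the same minute, so 6 of 10 could be 5 or 7. The inflation figures likewise rest on assumed AR(1) values and are small with few windows.

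A reader might infer that the analysis will lose 40% of the effect, that the trial is underpowered, or that this shows .82 to be wrong. The documents support none of these: they do not say that the main effect decides, and they do not tie d = 1 to the 5-30 minute mean.

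The remedy has limits too. A four-session omnibus test does not say which session differs. It also needs its own sphericity correction and a rule for which blocks count.

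**Conclusion.** The point holds as a worthwhile improvement to the analysis plan, not as an error in a stated number. The protocol's expected period and the SAP's test are not connected, and the deciding term is open.

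If the ten-block main effect is read, the cost in power is clear with one active session, moderate with two equal sessions in the same direction and negligible with equal opposite effects. If the interaction is read, power is mostly kept, but the effect in the expected period is not estimated and a sphericity correction is needed. Accepting either term costs about 10% type I error even with the correction.

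The power figures rest on dz = 1 for the 5-30 minute mean, a constant effect confined to that period, and 6 of 10 active blocks. Because 30 minutes is given as a maximum, the 60% share could be lower. Confidence is medium, since the documents give neither the correlation between blocks nor the directions of effect.

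**What to change.** For each task, name as primary a one-way repeated-measures test of session (cTBS, iTBS, control, sham). Use one value per participant and session: the mean baseline-subtracted threshold over the blocks of that task that start from 5 to 30 minutes after stimulation. Use the same block numbers in the control session, which has no stimulation time, and apply a Huynh-Feldt correction. Keep the session-by-window ANOVA as the secondary time-course analysis, with the windows defined and the same correction.

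This changes SAP wording only and needs no added testing. The price is that an effect outside 5-30 minutes would appear only in the secondary analysis. A shorter effect would still be partly diluted: for one lasting 5-20 minutes, the primary mean recovers 4/6 = 67%, against 4/10 = 40% over ten blocks.

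The rule should be fixed before session results are examined. The documents do not make clear whether data collection is finished. If results have already been seen, label the analysis post hoc.

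### The planned repeated-measures ANOVA drops any participant with an empty session-by-window cell; a mixed model would keep the sessions that were observed

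*Combined protocol and SAP*

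**What the plan says.** The Experiment 7 specific Methods describe a within-person design: "Participants will complete three TMS sessions (iTBS, cTBS, sham) and a fourth behavioral-only control session". On timing they state: "Each session will be separated by at least one week with the order counterbalanced across participants". Each TMS session has 3 baseline blocks and 10 post-stimulation blocks per task.

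The Statistical Analysis Plan says "We will compare the change in sensory acuity from pre- to post-TMS between sessions using a repeated measures ANOVA", and specifies that "a single repeated-measures ANOVA will be conducted for each task with sessions (cTBS, iTBS, control, sham) and time windows as independent variables". The outcome is the post-stimulation threshold minus the baseline threshold of the same session. The number and width of the time windows are not defined.

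The sample-size paragraph assumes d = 1 and concludes "Testing 17 participants gives a power of .82" at an alpha of 0.05. It does not say whether 17 counts people enrolled or people who finish all four sessions. Nowhere do the documents state an expected loss, a replacement rule, or what happens to a participant with a missed session or an unusable threshold.

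**The concern.** A classical repeated-measures ANOVA works on a full participant-by-cell table. If one cell is empty, the whole row is normally removed. Someone with three complete sessions and one missed session then contributes nothing, not even to a comparison between two sessions they did attend.

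Four visits at least a week apart give several opportunities for a missed visit, and the sample is small. Two things are at stake. The first is precision: data already collected from volunteers are not used. The second is validity: the result describes only those who completed everything, which can bias it if people who drop out respond differently from those who stay. A method that uses the partial data is readily available for this design.

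**Working it through.** **Inputs from the documents.** 17 participants, d = 1, alpha 0.05, power .82, four sessions per person, 10 post-stimulation blocks per task per session (assumed to apply to the control session too), 3 baseline blocks per task per session.

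**Inputs assumed.** Two-sided tests. Sessions missed independently with probability p. Exactly 17 enrolled and none replaced. The documents give no value for p, so a range is shown.

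**1. The plan's own figure.** The stated .82 is matched closely by two independent groups of 17 at d = 1: .830 by the normal approximation, .807 by the noncentral t. It is not matched by a paired comparison of 17 people with a within-person effect d_z = 1, which gives .972. The documents do not say which meaning of d applies, so two within-person effects are carried forward:
- d_z = 1, taking the stated d as the paired effect;
- d_z = 0.743, solved so that a paired t-test with n = 17 has power .82. This value is not in the documents.

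**2. Complete participants.** The expected number is 17(1 − p)^4. The chance that all 17 are complete is (1 − p)^68.

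| p per session | Expected complete | Chance all 17 complete |
|---|---|---|
| 1% | 17 × 0.9606 = 16.3 | 50% |
| 3% | 17 × 0.8853 = 15.0 | 13% |
| 5% | 17 × 0.8145 = 13.8 | 3% |
| 10% | 17 × 0.6561 = 11.2 | under 0.1% |

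For a contrast between two given sessions, the expected number of available pairs is 17(1 − p)^2: 17 × 0.9025 = 15.3 at 5% and 17 × 0.81 = 13.8 at 10%.

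**3. Power for one paired contrast.** The power of the two-sided paired t-test (noncentral t) is averaged over the binomial number of people retained. The retention probability is (1 − p)^4 for complete cases and (1 − p)^2 for available pairs.

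| Within-person effect | p | Complete cases | Available pairs |
|---|---|---|---|
| d_z = 1 | 5% | .92 | .95 |
| d_z = 1 | 10% | .84 | .92 |
| d_z = 0.743 | 5% | .72 | .77 |
| d_z = 0.743 | 10% | .60 | .72 |

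The available-pairs column is a simple guide to what keeping partial data is worth. It is not a simulation of the mixed model proposed below.

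**4. Unusable blocks.** Suppose 1% of blocks are unusable, independently.
- If each of the 10 blocks is its own window, there are 4 × 10 = 40 cells per task. The expected number complete is 17 × 0.99^40 = 11.4.
- If windows pool two blocks, there are 4 × 5 = 20 cells, each empty only when both blocks fail. The expected number complete is 17 × (1 − 0.01²)^20 = 17.0.

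The effect of a lost block therefore depends almost wholly on how the windows are defined, and the documents do not define them.

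**The case against.** The best defence is that the power claim need not suffer. With d = 1 as the paired effect, 11 complete participants give .848, and even 10% of sessions missed leaves .84 on average, above the stated .82. The drop to .72 or .60 appears only at a back-solved effect. This stands. A reader might infer that the trial has no margin and that any loss takes power below the plan's figure. The documents do not support that, because the stated .82 is not tied to the planned within-person analysis and the true margin is unknown.

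Other stronger readings also fail:
- **The ANOVA will probably not run on 17 people.** This needs an assumed loss rate and 17 meaning enrolled without replacement. The text can be read as 17 completers. The sessions have a minimum spacing and no stated maximum, so a missed visit could be rescheduled.
- **One unusable block removes a participant.** The ANOVA factor is the time window, and a lost block empties a cell only if it is alone in its window. With three baseline blocks per task, losing one need not void a session's baseline either.
- **Loss would break the counterbalancing.** 17 = 4 × 4 + 1, so a set of four orders could not be used equally often even with no loss.

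It is also true that no passage says incomplete participants will be discarded. That follows from how the named method normally works, and no alternative is given. A replacement rule, or enrolling more people, would protect the number of completers: 17/0.90 rounds up to 19 for 10% overall loss and 17/0.80 to 22 for 20%. Neither would recover the data of those who were only partly observed.

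**Conclusion.** The point holds as a weakness in the choice of analysis that is cheap to remedy. It does not show that the trial is underpowered. The method as named discards people with an empty session-by-window cell, and the plan has nothing to offset this.

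Under the assumed 5% and 10% session losses, keeping available pairs gains 3 and 8 percentage points of power at d_z = 1, and 5 and 12 points at d_z = 0.743 (differences of the rounded figures). The gain is present at both effect sizes; a fall below .82 occurs only at the smaller one. Possible completer-selection bias does not depend on the effect size, but the documents give no basis for putting a number on it.

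These sizes rest on independent misses, 17 enrolled without replacement, and a single unadjusted paired contrast standing in for the ANOVA.

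**What to change.** Replace the repeated-measures ANOVA with a linear mixed model for each task on the baseline-subtracted thresholds:
- fixed effects for session, time window and their interaction;
- random effects for participant and participant-by-session;
- Kenward-Roger degrees of freedom;
- every participant with at least one analysable session included.

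Keep the complete-case ANOVA as a sensitivity analysis. In the same edit, define the time windows, say whether 17 is the number enrolled or completed, and state whether people who leave are replaced.

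The cost is SAP wording and slightly more analysis work. The mixed model is valid if data are missing at random given what was observed; it does not protect against loss that depends on the unobserved thresholds. With complete data, the session comparison should be essentially that of the ANOVA. The window and interaction tests can differ somewhat, because the ANOVA uses separate error terms for them. A session-order effect and serially correlated residuals may be considered on their own merits, but they are optional and not part of the missing-data remedy.
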